4.2 Pharmacokinetic Evaluation based on Sparse Sampling Data

NKTR-181 concentration-time data at each dose level and study visit during Treatment period will be pooled from all subjects and described by descriptive statistics to evaluate trends in drug concentrations with dose and study visits. No formal statistical tests will be conducted. Furthermore, visual inspection of drug concentrations at each dose level and study visit will be performed. Only patients on a stable dose level will be included in the graphical analysis.

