5.2 Sparse Sampling PK Population

Subjects who received at least one dose of NKTR-181 and had at least one plasma sample will be included in the sparse sampling PK population. The PK analysis data set will include all plasma samples from all subjects with the following exceptions: Subjects with only pre-first dose NKTR-181 concentration available for the entire duration of the study and post-dose samples with BLQ concentrations.

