6.0 PHARMACOKINETIC DATA EVALUATION

6.1 Bioanalysis of Plasma Samples

Concentrations of NKTR-181, oxycodol, and oxycodone in plasma samples will be assayed using validated methods. NKTR-181 levels will be analyzed for both spare samples and PK subgroup samples. Oxycodol and oxycodone levels will be analyzed for the PK subgroup samples only.

For the purpose of the PK analysis, plasma concentration values reported as below the limit of quantification (BLQ) will be treated as zero for pre-dose samples. Plasma concentrations values reported as BLQ at all other times will be considered as missing. Concentration values in any sample matrix reported as NR (not received) or NA (not analyzed) will be treated as missing values.

Unreliable results, such as those arising from procedural errors during conduct of the study or analytical errors will not be used.

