6.3 Presentation of Individual and Mean Plasma Drug Concentrations and PK Parameters

6.3.1 Listings and Tables

Listings for blood collection dates and times will be generated by subject, and treatment. Sampling time deviations will be computed as differences between scheduled (nominal) and actual sampling times and expressed in minutes and as a percentage of the nominal time.

Plasma analyte concentrations at each nominal PK sampling time will be tabulated by treatment using descriptive statistics, including the number of observations (n), n listed as BLQ, arithmetic mean, geometric mean, standard deviation, standard error of the mean (SEM), CV%, median, minimum and maximum. Missing and BLQ concentration values will be treated using the criteria provided in Section 6.1. Missing concentration values will not be included in the descriptive statistics.

For the PK sub-study, plasma PK parameters will be listed by subjects and summarized by dose level using descriptive statistics, including, n, geometric mean, mean, standard deviation, CV%, median, minimum and maximum.

For sparse PK sampling, number of subjects and samples at each dose level and study visit will be tabulated and summarized using descriptive statistics, including, n, median, and range.

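### Leaving post-dose BLQ samples out of the sparse PK summaries raises the reported median and minimum wherever such samples occur, by an amount the documents do not allow us to state

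*SAP*

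**What the plan says.** All PKAP sections cited here are in the PK analysis plan contained in the SAP document.

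- **Purpose.** PKAP 4.2 pools every subject's sparse NKTR-181 concentrations by dose level and visit "to evaluate trends in drug concentrations with dose and study visits". It adds: "No formal statistical tests will be conducted". Only its graphical part is limited to patients on a stable dose.
- **Exclusion.** PKAP 5.2 takes two things out of the sparse data set: subjects whose only concentration precedes the first dose, and "post-dose samples with BLQ concentrations".
- **BLQ coding.** Under PKAP 6.1, BLQ values "will be treated as zero for pre-dose samples". For the rest: "Plasma concentrations values reported as BLQ at all other times will be considered as missing".
- **Tables.** PKAP 6.3.1 states: "Missing concentration values will not be included in the descriptive statistics". The sparse table, by dose level and visit, is "summarized using descriptive statistics, including, n, median, and range". A BLQ count ("n listed as BLQ") is named in a different paragraph, for tables by nominal sampling time and treatment.
- **Sub-study.** PKAP 5.1 also excludes subjects with pre-dose BLQ levels from its summary tables, but tabulates their number and percentage by dose level. The sparse set has no matching commitment.

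**The concern.** A BLQ result is not an absent result: it says that the concentration is below the assay limit. Treating it as missing selects on the outcome, because what remains in a cell is the detectable part of the distribution. The sparse analysis exists to show how concentrations move with dose and visit. A rule that trims the bottom of each cell by a different, unreported amount can distort that comparison. The median, which is the planned summary of location, can use BLQ values by rank alone, so nothing technical requires their removal.

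**Working it through.** **Inputs from the documents.** The exclusion and coding rules (PKAP 5.2, 6.1, 6.3.1), the sparse statistics (6.3.1) and the dose range of 100 to 600 mg BID (Protocol synopsis). The plan states no figure on this point, so there is none to reproduce. The LLOQ, BLQ rate, variability and half-life are not given.

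**Assumptions.** Log-normal concentrations, log-SD s = 0.5, 0.8 or 1.0; a fraction p of samples in a cell is BLQ and dropped.

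**Step 1: direction.** Removing only the smallest values cannot lower a median. It leaves a minimum at or above the LLOQ, apart from any pre-dose zeros kept under 6.1. This needs no distributional assumption.

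**Step 2: size.** The retained median is the p + (1 − p)/2 = (1 + p)/2 quantile of all samples. Under the log-normal,

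retained median / all-sample median = exp(s × z((1 + p)/2)).

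For p = 20% and s = 0.8: exp(0.8 × 0.2533) = 1.225. A simulation of 2,000,000 values gave 1.223.

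| p BLQ | (1 + p)/2 | z | s = 0.5 | s = 0.8 | s = 1.0 |
|---|---|---|---|---|---|
| 1% | 0.505 | 0.0125 | 1.006 | 1.010 | 1.013 |
| 5% | 0.525 | 0.0627 | 1.032 | 1.051 | 1.065 |
| 10% | 0.550 | 0.1257 | 1.065 | 1.106 | 1.134 |
| 20% | 0.600 | 0.2533 | 1.135 | 1.225 | 1.288 |

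**Step 3: what a dose trend could look like (illustration only).** Further assume a fixed LLOQ and a median proportional to dose. Then p(d) = Φ(z(p100) − ln(d/100)/s), where p100 is the BLQ fraction at 100 mg. With p100 = 20% and s = 0.8, p at 600 mg is Φ(−0.842 − 1.792/0.8) = Φ(−3.08), or 0.1%. The 100 mg median rises by 22.5% and the 600 mg median by 0.1%, so a true 6-fold ratio appears as 6 × 1.001/1.225 = 4.9 (5.3 at s = 0.5, 4.7 at s = 1.0). With p100 = 5% it appears as 5.8, 5.7 and 5.6 for s = 0.5, 0.8 and 1.0.

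**Step 4: what a visit trend could look like (illustration only).** Suppose a share q of samples at a visit is BLQ because no recent dose was taken. Relative to the median of the dosed subjects, the all-sample median is t = exp(s × z((0.5 − q)/(1 − q))), while the retained median stays at 1. For q = 10%, t is 0.933 to 0.870 over s = 0.5 to 1.0, an overstatement (1/t − 1) of 7.2 to 15.0%. For q = 20%, t is 0.853 to 0.727, an overstatement of 17.3 to 37.5%.

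**Step 5: the alternative.** With BLQ values kept and ranked lowest (p = 20%, s = 0.8), the simulated median was 1.001 against a true value of 1. This works while fewer than half of a cell's samples are BLQ; beyond that the median is itself below the LLOQ.

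**The case against.** **The target may be exposure while taking the drug.** Results are grouped by dose level, and a sample from someone not taking tablets does not describe that dose. This stands in part. The PKAP does not state such a target, and 4.2 pools all subjects. But PKAP 3.2 schedules sparse samples at unscheduled, end-of-treatment and early-termination visits, and Protocol 6.2 and 6.5 foresee interrupted dosing. Retaining every BLQ sample without condition would put off-drug samples into a nominal dose cell, so the fix has to separate them.

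**The scope of the rule is unclear.** PKAP 3.2 lists visits but no times relative to dose. If a clinic sample drawn before the morning tablet counts as pre-dose, 6.1 keeps its BLQ value as zero and the effect shrinks. The contrast in 5.2 with samples before the first dose suggests that post-dose means any time after it, but does not settle the matter. This stands, and is itself a reason to revise the text.

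**BLQ counts may be covered already.** The paragraph in 6.3.1 naming a BLQ count can be read as general. But it refers to nominal sampling times, and the separate sparse sentence does not repeat it. Even if it applied, the medians would still exclude BLQ values.

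**A stronger reading is tempting.** A reader might infer that the rule will hide falling adherence or diversion, or that low-dose medians will be the most inflated. The documents do not support either as a result. Whether a missed dose gives a BLQ sample depends on the LLOQ, the half-life and the time since the last dose, none of which is stated. Partial non-adherence can leave low but measurable values, which are kept. The low-dose gradient needs exposure to rise with dose against a fixed LLOQ, which is plausible but not shown. Adherence and diversion also have their own measures: tablet-count compliance (SAP 8.5) and MADDERS (SAP 8.7.4).

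**The consequence is small.** This stands: the sparse analysis is descriptive and has no tests.

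**Conclusion.** The point holds in a limited form. Where post-dose BLQ samples occur, the planned sparse summaries overstate the median and minimum relative to all samples collected, and comparisons across doses or visits may be distorted if BLQ frequency differs between cells. The direction follows from the rule itself. The size does not: under the log-normal assumption it runs from about 1% at 1% BLQ to 13.5 to 28.8% at 20% BLQ, and the documents give no basis for choosing a rate. A larger effect at low dose, or masking of complete recent non-dosing, is possible but not shown. The primary safety objective is untouched, and population PK has its own plan (Protocol 8.2). This is a minor but worthwhile correction.

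**What to change.** Amend PKAP 5.2, 6.1 and the sparse paragraph of 6.3.1 as follows:

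1. For samples taken while the subject is recorded as on study drug at that dose level, keep post-dose BLQ results and rank them lowest in the median. Report '<LLOQ' where the median or minimum falls there, and state the LLOQ.
2. Give n and % BLQ for each dose and visit.
3. Summarise separately the samples taken when dosing was interrupted or stopped.
4. Define pre-dose and post-dose for clinic-visit sparse samples.
5. Show the current exclusion as a sensitivity summary.

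The cost is some PKAP wording and table programming. No new assays are needed.

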6.0 PHARMACOKINETIC DATA EVALUATION

6.1 Bioanalysis of Plasma Samples

Concentrations of NKTR-181, oxycodol, and oxycodone in plasma samples will be assayed using validated methods. NKTR-181 levels will be analyzed for both spare samples and PK subgroup samples. Oxycodol and oxycodone levels will be analyzed for the PK subgroup samples only.

For the purpose of the PK analysis, plasma concentration values reported as below the limit of quantification (BLQ) will be treated as zero for pre-dose samples. Plasma concentrations values reported as BLQ at all other times will be considered as missing. Concentration values in any sample matrix reported as NR (not received) or NA (not analyzed) will be treated as missing values.

Unreliable results, such as those arising from procedural errors during conduct of the study or analytical errors will not be used.

6.2 Calculation of Plasma Drug Pharmacokinetic Parameters

All parameter values listed in Section 4.0 will be determined by non-compartmental analysis. PK parameter calculations will be based on the actual sampling times. Calculation of AUC will be performed using linear trapezoidal rule.

6.3 Presentation of Individual and Mean Plasma Drug Concentrations and PK Parameters

6.3.1 Listings and Tables

Listings for blood collection dates and times will be generated by subject, and treatment. Sampling time deviations will be computed as differences between scheduled (nominal) and actual sampling times and expressed in minutes and as a percentage of the nominal time.

Plasma analyte concentrations at each nominal PK sampling time will be tabulated by treatment using descriptive statistics, including the number of observations (n), n listed as BLQ, arithmetic mean, geometric mean, standard deviation, standard error of the mean (SEM), CV%, median, minimum and maximum. Missing and BLQ concentration values will be treated using the criteria provided in Section 6.1. Missing concentration values will not be included in the descriptive statistics.

For the PK sub-study, plasma PK parameters will be listed by subjects and summarized by dose level using descriptive statistics, including, n, geometric mean, mean, standard deviation, CV%, median, minimum and maximum.

For sparse PK sampling, number of subjects and samples at each dose level and study visit will be tabulated and summarized using descriptive statistics, including, n, median, and range.

6.3.2 Plots

The following plots will be generated for the PK sub-study population:

Plots of individual plasma NKTR-181, oxycodol, and oxycodone concentration versus actual time on linear and semi-log scales for each subject by treatment.

Overlay plots of mean (\pm SEM) plasma NKTR-181, oxycodol, and oxycodone concentrations in each treatment versus nominal time on linear and semi-log scales.

Overlay plots of mean (\pm SEM) concentration versus nominal time for all treatments by analyte on linear and semi-log scales

Spaghetti plots of individual plasma concentration versus nominal time for all subjects by treatment by analyte on linear and semi-log scales

The following plots will be generated for the sparse PK population:

Plots of plasma NKTR-181 concentrations by dose and study visit for subjects who enter the Stable dose Treatment Period.

6.4 Reporting Conventions

Rounding for the reporting of PK parameters will be 3 significant figures except C_{max} and AUC for NKTR-181 oxycodol, and oxycodone which will be rounded to 4 significant figures. The same convention will be followed for descriptive statistics, except for n, which will be rounded to the whole value. Descriptive statistics will not be performed if $n < 3$ and summary tables will only include median, minimum, and maximum. Percentages presented in tables will be rounded to one decimal place. If “%” is part of the column heading, do not repeat the “%” sign in the body of the table.

